[figure not shown]

**Summary of changes**

1. Clarification on the events to be counted as fractures
2. Final update on fracture inclusion, now expanded to include ribs, sternum, facial, cranial and some types of vertebral fractures.
  - Selection of fractures to be reported separately
  - Definition of fracture dates
  - Definition of fracture episodes
  - Fractures over a longer time period
  - Addition of SAP disclaimer
  - Final definitions of compliance
3. Rules for hierarchy of tests revised to ensure consistency with the contract from the funder and original protocol.

## **2. AIM AND DESIGN OF THE PreFIT TRIAL**

This section outlines the study design for the PreFIT trial.

### **2.1 Objectives**

The aim of the PreFIT trial is to estimate the comparative effectiveness and relative cost-effectiveness of three primary care fall prevention interventions.

The trial will contribute a substantial body of evidence to inform UK healthcare practitioners, commissioners and other stakeholders on the relative effectiveness and cost effectiveness of a range of primary care options for preventing falls and fractures.

### **2.2 Study Design and interventions**

- A pragmatic, multi-centre cluster randomised controlled trial.
- Unit of randomisation is the general practice.
- The study will investigate a primary prevention screening strategy investigating the effectiveness and cost-effectiveness of three alternate interventions (advice, exercise, multifactorial falls prevention programme (MFFP)).
- This is a superiority trial which will recruit a minimum of 9,000 community dwelling people aged 70 years and older.

### **2.3 Eligibility criteria**

#### **2.3.1 General practice inclusion criteria**

General practices will be eligible to participate in the trial if they meet all of the following criteria:

- Located in the region that has the infrastructure to provide the active interventions;
- Technical capability for electronic searching, extracting and reporting of aggregated and individual-level data;
- Agree to adhere to a randomly allocated intervention and to support research staff in the execution of the research protocol.

### 2.3.2 Participant inclusion criteria

Participants will be eligible to participate in the study if they meet all of the following criteria:

- Provided a signed informed consent form;
- Aged 70 years or over ;
- Live in the community, including living in sheltered or supported accommodation.

### 2.3.3 Participant exclusion criteria

- Participant will not be eligible to participate in the trial, if they meet any of the following criteria:
- Live in residential care or nursing home;
- Limited life expectancy (< 6 months) as determined by GP.

## 2.4 Randomisation

- Unit of randomisation is the general practice.
- The Warwick Clinical Trials Unit programming team will generate the randomisation. The clusters are allocated to the interventions by the data management team
- General practices will be randomly allocated in blocks of three with one of the three trial treatments. There is no stratification and the method of randomisation is minimisation by general practice.
- Practices will be randomised simultaneously when the initial record searches have been completed and the sample identified and enrolled (400 participants screened and contacted to obtain a sample of 150 enrolled trial participants) at all three practices in each block.

## 2.5 Blinding

- It is not possible to blind participants to the treatments they are receiving or to blind the health care professionals delivering the interventions. Participants were 'blinded' to the alternative treatment options.
- Researchers responsible for data entry and analysis will be blinded to the allocation.

- In addition assessment of the primary outcome will be blinded when data are drawn out of HES and data on 'suspected' fracture events will be validated by researchers who are blind to the cluster allocation.

As we have developed methods for extracting data from both Hospital Episode Statistics and GP records it is apparent that reporting is sufficient to be able to distinguish fall related versus non-fall related compression fractures of the vertebral column. We will include vertebral fractures from HES and GP records where these are consistent with a trauma mechanism (there is a clear description of trauma/fall or the fracture presentation is consistent with trauma and maps to the ICD-10 codes being generated from HES as detailed in Appendix 1). Reports of vertebral osteoporotic compression fractures in GP records will be excluded unless clearly linked to a report of trauma/fall.

All fractures that are ascertained in GP record searches will be assigned a code and data similar to the coding framework and definitions used in ICD 10 2010 version, and as outlined in Appendix 1. The search strategy used for GP READ code searching is provided in Appendix 3/available from study team.

We have updated the list of fractures to include the face and cranium as reported in Bruce et al (2016). We will also include rib fractures as these were omitted from the published protocol.

### ***Secondary outcomes***

Secondary outcomes will encompass the following:

- *Fracture rate per person month of observation for the entire available period of observation*

We have collected additional data on fractures from HES for a time period that extends beyond 18 months after randomisation. This data will also be summarised and analysed.

- Proportion of people sustaining one or more fracture over 18 months

- Time to first fracture

We will attempt to date all fractures. The date of fracture will be taken as the A&E attendance or HES episode admission date where these exist. In addition, we will check GP records for confirmation of fracture dates where these are recorded, with the exact date of fracture event if reported taking precedence over HES and A&E attendance if these differ.

- Fracture episodes

It is possible that people will experience multiple fractures from one fall. It will not be possible to consistently attribute fractures to a single fall event. Instead we will estimate fracture episodes. We will characterise all the fractures occurring on the same date as one episode. We will use statistical modelling to account for fractures occurring in the same individual and in the same episode. We will report and explore the number of episodes of fractures and recurrent fracture episodes. We may not be able to generate sufficient resolution in the data to assign fractures to episode. If so, we will not report these data (this will be apparent after the data cleaning is finalised).

- Fracture regions

We will estimate the difference in number of proximal femoral fractures (hip fractures) and fractures involving the distal radius (wrist fractures). Hip fractures were defined as verified fractures with a specific description of neck of femur or proximal femur. Fractures described as subtrochanteric, femoral shaft, distal femur, or simply femoral will not be categorised as hip fractures.

- Falls rate per person per month observation over the 18 months

- Proportion of people sustaining one or more fall over the 18 months
- mobility/ADLs:  
Questions on difficulties balancing on a level surface, ability to walk outside of the house, and average time spent walking.
- Frailty:  
A 16 item frailty questionnaire. We will report sub-domains and the overall domain scores for the follow up time points in which we have these data.
- Cognitive ability:  
A clock-drawing test used as for cognitive screening.
- Health related quality of life:  
EQ-5D and SF12 sub-domain and overall scores.
- Resource use  
Routine Hospital Episode Statistics (HES) data and CRF data  
Unit cost data

### **Process variables**

- Uptake of the intervention(s)
- Compliance with the intervention including medication prescriptions where available, attendance at exercise sessions, attendance at MFFP assessment.

## **Safety**

- Serious adverse events and adverse events will be reported.

### **2.7 Planned sample size**

The primary outcome is the fall related fracture rate, expressed as the fracture rate per person per unit time of observation over 18 months after randomisation of the General Practice.

In the UK, the annual fracture incidence per 100 men aged 55-74 years is 2.6 (95% CI 1.9 to 3.3); this rises to 7.6 fractures (95% CI 4.0 to 11.3) per 100 women aged of the same age range over 55 years (Donaldson et al, 2008).

Adjusting for differences in gender in the general population (ONS 2006) yields a fracture rate of 6 per 100 people (6%) aged over 70 years. This estimate does not account for repeat fractures within a person and hence is a conservative estimate of the fracture rate.

To have 80% power to detect, as significant ( $p < .05$ ), a 2% reduction in fracture rate, from 6% to 4% (relative risk reduction, 0.67), requires 1900 participants per arm, or 5,700 overall. Incorporating a design effect to adjust for varying degrees of modest clustering (ICC range .001 to .003), inflates the sample size estimate to 7800, or 2,600 per arm. Allowing for 10% loss to follow-up, yields a target sample size of 9,000 participants. To recruit 9,000 participants at 150 per practice requires 60 general practices.

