## **6. STATISTICAL ASPECTS**

The statistical analyses will be carried out using SAS (version 9.13).

All statistical tests will be two-sided and performed at the 5% significance level.

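### The sample size in SAP 2.7 applies annual fracture incidences to an 18-month outcome without conversion, so the stated 80% power describes a 12-month comparison

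*SAP*

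**What the plan says.** Section 2.7 of the SAP opens with the primary outcome, "expressed as the fracture rate per person per unit time of observation over 18 months". The inputs that follow are yearly: "the annual fracture incidence per 100 men aged 55-74 years is 2.6", and "this rises to 7.6 fractures (95% CI 4.0 to 11.3) per 100 women". A gender adjustment then "yields a fracture rate of 6 per 100 people (6%) aged over 70 years". The calculation reads "To have 80% power to detect" a 2% fall, "from 6% to 4% (relative risk reduction, 0.67), requires 1900 participants per arm, or 5,700 overall". Clustering (ICC 0.001 to 0.003) raises this to 2,600 per arm, and 10% loss brings the total to 9,000, at 150 per practice.

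Section 4.2 says that the calculation rests on the proportion with at least one fracture, and section 2.6 places that proportion, like the primary rate, over 18 months. Section 6 fixes the test: "All statistical tests will be two-sided and performed at the 5% significance level".

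The only caveat offered on the 6% is that it ignores repeat fractures. Nothing is said about its time base.

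**The concern.** The 6% is built from annual figures and is then used as the control proportion for an outcome observed half as long again. If fractures keep occurring at the plan's rate, more than 6% of controls will have one by 18 months. The proportions compared, and hence the power, are not those of the planned analysis.

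Section 2.7 is where a reader will look to interpret the result, above all a null one. It should say which effect, over which period, the trial could detect with what probability. As written, it gives a power for a comparison that the trial does not make. Section 4.2 also plans to assess how the observed ICC affects the sample size, so the calculation will be revisited and needs the right base proportion.

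A smaller fault sits in the same sentence: going from 6% to 4% is a relative risk of 0.67, and the relative reduction is 0.33.

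**Working it through.** **Inputs.** From 2.7: 6% v 4%, 80% power, 1,900 per arm before clustering, 2,600 per arm after it, ICC 0.001 to 0.003, 150 per practice. From section 6: two-sided 5%. Assumption, because the SAP gives no 18-month rate: a constant fracture rate.

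**1. The plan's own figure.** With pooled variance and no continuity correction,

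n = [1.960 × √(2p̄(1−p̄)) + 0.8416 × √(p₁q₁ + p₂q₂)]² / (p₁−p₂)².

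For 0.06 v 0.04, p̄ = 0.05, so n = [1.960 × 0.3082 + 0.8416 × 0.3079]² / 0.0004 = 1,863. This agrees with the plan's 1,900, at which power is 0.81. The arithmetic from 6% v 4% is sound; the fault is in the time base of the input.

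**2. Is the 6% annual?** It is described as a gender-weighted version of 2.6 and 7.6 per 100 per year, and it lies between them. Carried to 18 months the inputs would be 3.9 and 11.4. A weighted value of 6 would then need (6 − 3.9)/(11.4 − 3.9) = 28% women, which is hard to credit for people over 70. The text describes no such scaling.

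**3. Conversion to 18 months.**
- Events: 6 × 1.5 = 9 and 4 × 1.5 = 6 per 100.
- At least one fracture, with 6 and 4 as rates: 1 − exp(−0.09) = 8.6% and 1 − exp(−0.06) = 5.8%. Applying the ratio 2/3 directly to 8.6% gives 5.7%.
- At least one fracture, with 6% and 4% as annual risks: 1 − 0.94^1.5 = 8.9% and 1 − 0.96^1.5 = 5.9%.

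**4. Effective size.** The design effect is 1 + 149 × ICC, or 1.149 at 0.001 and 1.447 at 0.003. So 2,600 per arm is worth 2,600/1.149 = 2,263 down to 2,600/1.447 = 1,797. The plan's 1,900 corresponds to an ICC near 0.0025 (2,600/1,900 = 1.368).

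**5. Power.** Power = Φ{[(p₁−p₂) − 1.960 × √(2p̄(1−p̄)/n)] / √((p₁q₁ + p₂q₂)/n)}. Example, 9% v 6% at n = 1,900: (0.03 − 1.960 × 0.008546)/0.008532 = 1.553, and Φ(1.553) = 0.940.

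| Comparison | Power at 1,900 effective | Power at 2,600, ICC 0.003 to 0.001 |
|---|---|---|
| 6% v 4% (as printed) | 81% | 79-87% |
| 9.0% v 6.0% | 94% | 93-97% |
| 8.9% v 5.9% | 93% | 92-96% |
| 8.6% v 5.7% | 93% | 92-96% |
| 8.6% v 5.8% | 91% | 90-95% |

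**6. Cross-check on the rate scale.** The primary outcome is a rate modelled with an offset (6.3.2.2). For a simple Poisson comparison of 0.06 v 0.04 per year, with 2,600 per arm and the same design effects, SE(log ratio) = √[DE × (1/(n × 0.06 × t) + 1/(n × 0.04 × t))]. Power is 76-85% with t = 1 year and 90-96% with t = 1.5 years, which is the same picture.

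**The case against.** The strongest reply is that the omission does no harm. If 6% is annual, so are the 4% and the 2-point gap. On 18 months all three scale together, to 9 v 6 per 100, and power exceeds 80%. The primary outcome is a rate, so the effect estimated is a rate ratio, which does not change with the length of follow-up under a constant rate. The fix changes neither recruitment nor analysis. All of this stands, and it settles the direction. It does not make the printed power the right one for the outcome.

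Two stronger readings are tempting.

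- A reader might infer that the trial is underpowered for the 2-point reduction. This follows only if the control risk is scaled to 18 months while the 2 points are not: 9.0% v 7.0% or 8.6% v 6.6% gives 62-64% at 1,900 effective per arm, and about 60-72% at 2,600 over the ICC range. The section 4.2 statement that the calculation rests on a proportion permits a fixed 18-month risk difference as the target, but the SAP nowhere states one.
- A reader might infer that 6 cannot be obtained from 2.6 and 7.6 with a realistic share of women. The figure is printed without decimals, and any share from 58% (5.5) to 78% (6.5) rounds to 6. The population weights come from a cited source that the SAP does not reproduce, so no error is shown there.

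**Conclusion.** The point holds as a fault in what section 2.7 states. Its 80% belongs to a 12-month comparison of 6% with 4%. For the 18-month outcome, on the plan's own rates, power for a ratio of 0.67 is about 91-94% at 1,900 effective per arm and about 90-97% across the stated ICC range. The error is conservative for that target, and the documents do not support a claim that the trial is too small.

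This rests on three assumptions: a constant fracture rate over 18 months, 6% and 4% as annual figures (as the text reads), and the ratio as the target. If instead 6% v 4% was meant as an 18-month risk, the 80% stands, but the control rate is then about 4 per 100 person-years (0.06/1.5), which does not match the 6 obtained from the quoted annual inputs. The 0.67 label is wrong on any reading, though the 6% and 4% beside it limit the harm.

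**What to change.** Keep the target of 9,000 and revise the wording of section 2.7:

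- State the time base of the 6% and the 4%.
- If they are annual, restate them for the outcome: 6 v 4 per 100 person-years, 9 v 6 per 100 over 18 months, about 8.6-8.9% v 5.7-5.9% with at least one fracture, with the constant-rate assumption named.
- Give the power for a ratio of 0.67 over 18 months across the ICC range (about 90-97% at 2,600 per arm) in place of the single 80%.
- If they were meant as 18-month risks, say so, and explain how about 4 per 100 person-years squares with the quoted annual incidences.
- Say whether a fixed 2-point difference in 18-month risk is the target. Only if it is should the corresponding power (about 60-72%) be quoted.
- Write 'relative risk 0.67 (33% relative reduction)'.

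The cost is a paragraph of SAP text. Recruitment and the planned analysis are unaffected.

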### **2.8 Planned subgroup analyses**

We have selected sub-group criteria using simple data available in primary care. We will run confirmatory sub-group analyses on fracture outcomes for the following:

- **Age:** We will examine whether interventions are best targeted to the oldest old ( $\leq 80$  years or  $\geq 81$  years).
- **Gender:** There is considerable excess risk of falling and fracture in women.
- **Previous history of falls in the last 12 months:** This is not well recorded in primary care, and hence will depend on self-report;
- **Frailty:** This will be based on the categorisation of the Strawbridge questionnaire - not frail (rarely or never/sometimes) versus frail (often/very often).

- **Cognitive impairment:** If there are sufficient numbers of people scoring less than 5 on the cognitive impairment sub-test, we will run a sub-group analysis with cut-points less than 5 or 5 or more.

### 3. PLANNED INTERIM ANALYSIS AND THE ROLE OF THE IDMC

- A document detailing the framework of operational and statistical futility was compiled during the pilot stages. This document detailed the challenges that the trial faces in carrying out a formal futility analysis after the pilot was complete or during the main trial.
- No formal futility analysis was carried out at the end of the pilot stage.
- The responsibilities of the Independent Data Monitoring Committee (IDMC) are to monitor the data and make recommendations to the TSC on ethical or safety issues arising and to ensure the safety, rights and well-being of trial participants. The IDMC will consider the need for interim analysis and consider data emerging from other related studies. Provide information on the data obtained if requested by the Chief Investigator, TSC, Trial Sponsor or Trial Funder if further funding is required for the trial to continue.
- The IDMC will meet at least annually, or more often as appropriate, and meetings should be timed so that reports can be feed into the TSC.
- They IDMC, TSC and funder reviewed the pilot data and considered the trial viable.

## **4. MONITORING OF THE TRIAL**

Monitoring of the trial is a continual process, from the start to the end of the study. At the end of the trial two aspects related to monitoring will be examined:

- (a) Operational (logistical) and Process Management monitoring from top level down (i.e. region, general practice and participant level);
- (b) Monitoring – recruitment, retention and uptake of the intervention.

### **4.1 Operational (logistical) and Trial Management of Regions**

- There are 5 regions recruiting participants to the PRE-Fit trial: Devon, Warwickshire / Herefordshire, Worcestershire, Cambridge and Newcastle.
- Within the regions are the general practices. These general practices are randomised in clusters of 3, and within each general practice all participants are allocated to the randomised intervention.

### **4.2 Operational (logistical) and Trial Management monitoring of General Practices**

#### **Number and size of general practices and its impact on the Sample Size**

- The primary outcome is fractures, expressed as the fracture rate per person unit time of observation.
- The unit of randomisation is general practice. It is likely that the primary outcome may not necessarily be distributed in the same way across all the general practices – some general practices may be more likely to have a greater rate of fractures and others less. To allow for the different degrees of ‘clustering’ of fracture rates across the general practices, we compute the intra cluster correlation (ICC) coefficient.

- The sample size is based on the proportion of participants having at least one fracture. This would suggest that to assess the ICC, for a given participant, we have a binomial distribution of a fracture (1) or no fracture (0) and we use methods stated by Chakraborty et al, 2009. Proc GLIMMIX (using link=logit distribution=binomial) will be used to estimate the ICC.
- The parameters which are required to obtain the ICC will be summarised. These include the number of general practices, the number of participants within each general practice, the number of participants with at least one fracture (primary outcome) within each general practice, the number of fractures. These parameters will be used to obtain the ICC and we will assess its impact on the overall sample size.

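### Section 4.2 of the SAP names no trial-arm term in the ICC model; read as written, the ICC absorbs any treatment effect and could make the sample look too small

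*SAP*

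**What the plan says.** Section 2.7 starts from 6% v 4% with 80% power; this "requires 1900 participants per arm, or 5,700 overall". The next step is worded "Incorporating a design effect to adjust for varying degrees of modest clustering (ICC range .001 to .003") and takes the figure to 2,600 per arm, 7,800 in total. Allowance for 10% loss gives a target of 9,000, recruited as 60 practices of 150.

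Section 4.2, under the sub-heading on the number and size of practices, returns to clustering. It treats the outcome as binary (any fracture or none), refers to a cited method, and adds: "Proc GLIMMIX (using link=logit distribution=binomial) will be used to estimate the ICC". It lists what is needed: how many practices there are, how many participants and how many fracture cases each has, and how many fractures occurred. It closes with: "These parameters will be used to obtain the ICC and we will assess its impact on the overall sample size".

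Trial arm is not in that list, and no fixed effect is given for the model. The covariates in section 6.3.2.1 belong to the outcome models, and nothing carries them over to the ICC.

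**The concern.** The practice is the unit of randomisation, so every participant in a practice is in the same arm. A difference between arms is therefore also a difference between practices. A model with a practice random effect and no arm term has nowhere to put that difference except the practice variance.

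The design effect in section 2.7 inflates a comparison of two arms. The ICC it needs is the correlation within an arm, after the arm difference has been removed. A pooled ICC is a different quantity, and it grows with the success of the interventions. At stake are the sample-size assessment that section 4.2 promises and any later use of the reported ICC.

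**Working it through.** **Inputs.** From section 2.7: 6% v 4%, 80% power, 1,900 per arm before clustering, ICC .001 to .003, 10% loss, 9,000 recruited, 60 practices of 150. From section 6: two-sided 5% tests. Assumptions: 20 practices per arm, equal practice sizes, and 135 analysed per practice (150 × 0.9).

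**The plan's own figures.** The two-proportion formula for 6% v 4% gives 1,863 per arm, consistent with the rounded 1,900. With design effect DE = 1 + (m − 1) × ICC, m = 150 and ICC = 0.0025, DE = 1 + 149 × 0.0025 = 1.3725, and 1,900 × 1.3725 = 2,608, which matches 2,600. So 0.0025 is a fair working value for the planned ICC. After 10% loss, 9,000 × 0.9 / 3 = 2,700 analysed per arm.

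**What a pooled ICC adds.** Let s be the variance of the three arm proportions divided by p(1 − p), where p is their mean. The pooled ICC is then s + ρ(1 − s), where ρ is the true within-arm ICC.

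- 6/4/4%: variance 0.0000889, p = 0.0467, p(1 − p) = 0.0445, s = 0.0020.
- 6/6/4%: variance 0.0000889, p = 0.0533, p(1 − p) = 0.0505, s = 0.0018.
- 6/5/5%: variance 0.0000222, p = 0.0533, p(1 − p) = 0.0505, s = 0.0004.

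**Effect on the implied sample size.** Need per arm = 1,900 × (1 + 134 × ICC), against 2,700 available.

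| True ICC | Within-arm need | Pooled, 6/4/4% | Pooled, 6/6/4% | Pooled, 6/5/5% |
|---|---|---|---|---|
| 0.001 | 2,155 | 2,663 | 2,602 | 2,267 |
| 0.0025 | 2,536 | 3,044 | 2,984 | 2,648 |
| 0.003 | 2,664 | 3,171 | 3,111 | 2,776 |

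For example, at a true ICC of 0.0025 and 6/4/4%, the pooled ICC is 0.0020 + 0.0025 × 0.998 = 0.0045. DE is 1.602 instead of 1.335. The implied recruitment is 3,044 × 3 / 0.9 = 10,146, instead of 8,455.

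If 150 rather than 135 per practice is used in the design effect, the same case moves from 2,608 to 3,172 per arm.

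**Sampling variation.** The ICC that uses up 2,700 per arm is (2,700 / 1,900 − 1) / 134 = 0.0031. In a beta-binomial simulation (60 practices of 135, 6/4/4%, 4,000 runs, analysis-of-variance ICC on the proportion scale), the estimate exceeded 0.0031 as follows:

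| True ICC | Pooled | With arm |
|---|---|---|
| 0.001 | 44% | 9% |
| 0.0025 | 71% | 34% |
| 0.003 | 77% | 43% |

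The mean estimates with arm were 0.0010, 0.0025 and 0.0030, so adding arm removes the bias but not the noise.

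**Scale.** Section 4.2 uses a logit link. If the ICC were read off the latent logit scale, σ² / (σ² + 3.29), the 6/4/4% contrast alone would contribute 0.0404 / (0.0404 + 3.29) = 0.012. Even with arm in the model, a true proportion-scale ICC of 0.0025 at p = 4.67% corresponds to σ² of about 0.0025 / 0.0445 = 0.056, and so to 0.056 / (0.056 + 3.29) = 0.017. Such a figure cannot be set against .001 to .003.

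**The case against.** The strongest objection is that the omission is inferred. Section 4.2 names a procedure, a link and a distribution but gives no fixed effects either way. Its list is worded as non-exhaustive and includes the number of fractures, which a 0/1 model does not use. The method is referred to a cited source that is not at hand. This stands: the SAP does not say that arm is excluded. But it does say that the listed quantities will be used to obtain the ICC, arm is not one of them, and the two possible models give materially different answers. Analysts are also blinded to allocation (section 2.5), which makes a pooled calculation a natural reading.

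A reader might infer that the trial would be declared undersized because an intervention worked. The SAP does not support that. It states no threshold, verdict or action, and section 4 places the monitoring review at the end of the trial. Nor does the arithmetic force it. At a true ICC of 0.001 and 135 per practice, the expected pooled figure still fits within 2,700, and at 6/5/5% it fits up to a true ICC of 0.0025.

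A reader might also infer that the treatment comparison is biased. It is not: section 6.3.2.2 fits practice as a random effect in the outcome models and does not draw on the section 4.2 ICC.

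Finally, the simulation used an analysis-of-variance estimator, not the SAP's mixed model. The exceedance percentages are therefore indicative; the expected additions of 0.0018 to 0.0020 are algebraic on the proportion scale.

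**Conclusion.** The point holds in a limited form. As written, section 4.2 describes an ICC pooled over arms, which is not the quantity that the design effect in section 2.7 requires. If the planned effect is real, the pooled ICC is too high by about 0.0018 to 0.0020. At a true ICC of 0.0025 and with both interventions effective, that is enough to turn a sufficient sample into an apparent shortfall of about 340 per arm (3,044 − 2,700). With no effect the error vanishes, and with a small one it is minor.

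The damage is confined to the clustering and sample-size assessment and any reuse of the ICC. The figures rest on equal practice sizes, 20 practices per arm, 135 analysed per practice, and an ICC on the proportion scale.

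**What to change.** In section 4.2, state that:

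- the ICC is estimated with trial arm as a fixed effect, coded A/B/C so that analysts stay blinded;
- it is reported on the proportion scale, so that it can be compared with the .001 to .003 in section 2.7;
- it is given with a 95% CI, because the estimate is noisy at 60 practices even with arm included;
- this within-arm value is the one used when the sample size is assessed.

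The cost is a few lines of SAP wording, one model term and a conversion of scale. No data collection or participants are affected.
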